# Figure 11–2 Control Article Diagrams

### Control Article 1

### Control Article 2

Document: TDOC-0050176 Version: 2.0; Effective; CURRENT

Status: Effective Page 35 of 75

### 11.2 Usage

The approved surgical products employed in this study will be utilized in accordance with approved indication(s). Refer to the system operator manuals and consumable surgical pack DFUs for in-depth instructions.

### 11.3 Accountability Procedures

The Investigator or the designee will order/ procure the clinical supplies (surgery packs, BSS Bags and other surgery-related ancillary supplies) and Alcon will reimburse the costs on an actual basis (if available, copies of the invoices and/ or order forms should be filed in the Investigator's clinical trial records for the Clinical Site Manager or any other Sponsor-personnel to review during the monitoring visits).

Upon receipt of study products, the Investigator or designee will conduct an inventory. Alcon will provide the site with accountability logs which will can be used to capture information on the subject ID, pack lot/ batch number, expiry date, date of dispensation, name of dispenser and will also have a column for 'sticking' the labels from the surgery packs. The Clinical Site Manager will train the site on appropriately completing this log.

The Investigator or the designee should follow the manufacturer's instruction on the storage-specifications of the supplies.

During the study, the site must maintain records (either in the Alcon provided log or site-specific logs) of study article dispensation and collection for each subject. The accountability log or any similar record must be made available to the study monitor for the purposes of verifying the accounting of clinical supplies.

Any discrepancies and/or deficiencies between the observed disposition and the written account must be recorded in the source notes along with a detailed explanation.

At the conclusion of the study, the Clinical Site Manager will perform a final reconciliation of the accountability records. The Investigator will be responsible for the collection of all unused supplies unless otherwise instructed by the Sponsor.

Throughout the study, the Investigator will be responsible for the accounting of all study products and will ensure that the study products are not used in any unauthorized manner.

*NOTE:* Over-labeling is not required as the site staff are all unmasked for this study.

**Document:** TDOC-0050176 **Version:** 2.0; Effective; CURRENT

Status: Effective Page 36 of 75

### 12 CLINICAL TRIAL PROCEDURES

### 12.1 Clinical Trial Assessments

The following section describes in general the assessments to be performed in this clinical trial. Assessments are thoroughly described in the Manual of Procedures (hereto MOP). Refer to section 6 SCHEDULE OF VISITS for an overview of assessments by visit.

NOTE: All ocular assessments are to be performed on the study eye only. Refer to section 10 SUBJECT POPULATION for information on study eye selection.

# 12.1.1 Pre-operative visit (Visit 0; Day -60 to Day 0)

Conduct pre-screening, screening and assign patient screening number as follows:

#### **12.1.1.1 Pre-Screen**

Where permitted by national and local laws and regulations, pre-screen all potential cataract patients via chart review. Additionally prescreen patients spontaneously presenting for cataract evaluation and/or annual examinations. In both cases, prescreen inclusion/exclusion criteria based upon routine testing conducted for all cataract patients.

**NOTE:** Prior to undertaking study specific testing, informed consent is required.

### 12.1.1.2 Informed Consent

Refer to Section 16.2: Informed Consent Procedures for specifics regarding informed consent process. For patients that pass pre-screening, explain the nature of the study. If the patient is willing to participate, appropriately consent the potential study subject and have him/her sign and date the Institutional Review Board (IRB) or Ethics Committee (EC) approved Informed Consent Document (ICD). If the patient is unable to comprehend and sign the ICD, he/she is not eligible for the study. Assign the potential subject a screening number (refer to Section 12.1.1.3 below) prior to any study specific testing.

**NOTE:** The subject's medical record must indicate participation in this study and desire to continue participation in the study.

# 12.1.1.3 Subject Number Assignment

Once the patient has been formally consented, the relevant patient information should be entered in the EDC system (Medidata® Rave) and the system will assign the subject number sequentially starting with etc.

**Document:** TDOC-0050176 **Version:** 2.0; Effective; CURRENT

Status: Effective Page 37 of 75

# 12.1.1.4 Demographics, Medical History and Concomitant Medications

Document demographics, ocular and non-ocular medical history, ocular and non-ocular concomitant medications and pregnancy status (where applicable). Refer to MOP for further instruction.

Ensure pregnancy status is documented for all women of child-bearing potential. Compare with Inclusion/Exclusion criteria (refer to *Section 10: Subject Population*). Identify potential safety issues for subject if enrolled in the study.

Record all concomitant medications for ocular and non-ocular conditions used by the subject at the time of the examination. No study specific medications are required for this study. The medications used during the trial are those that the Investigator deems necessary for cataract surgery procedures and treatment.

**NOTE:** Routine preoperative and intra-operative medications do not require capture.

#### 12.1.1.5 Inclusion/Exclusion Criteria

Refer to the list of Inclusion/Exclusion criteria in *Section 10: Subject Population*. Ensure the subject meets all requirements for participation and eligibility; ie meets all the inclusion and none of the exclusion criteria.

## 12.1.1.6 Selection of Study Eye

The study eye should be the eye with the worse cataract as indicated by LOCS II assessment. Where cataract grade is the same in both eyes, the right eye should be chosen as the study eye. Record the assigned study eye in the medical notes.

## 12.1.1.7 Visual Acuity (UCDVA and BCDVA) Testing

Perform Uncorrected Distance Visual Acuity (UCDVA) testing and Best Corrected Distance Visual Acuity (BCDVA) testing with study specified equipment. Refer to MOP for further instruction.

Ensure UCDVA and BCDVA testing precedes IOP measurement, the administration of eye drops to dilate or anesthetize the eyes, or any examination requiring contact with the eye.

*NOTE:* Lighting conditions must be measured and recorded prior to VA testing.

**Document:** TDOC-0050176 **Version:** 2.0; Effective; CURRENT

Status: Effective Page 38 of 75

## 12.1.1.8 Intraocular pressure (IOP)

Measure IOP using Goldmann or other applanation method. For each subject, the same instrument type should be used for all measurements in the study.

## 12.1.1.9 Specular Microscopy

Utilize a commercially available specular microscope (Konan microscope) to photograph the corneal endothelial cells as per the instructions provided by the Reading Center. Detailed information on transmission of the images to the reading Center for analysis is provided in the MOP.

**NOTE:** If the subject has been dismissed prior to assessment of image quality (not recommended) and images are of poor quality, the subject will be asked to return and the assessment will be repeated.

## 12.1.1.11 Slit-lamp Examination

Examine the anterior segment of the eye, including the eyelid, sclera, conjunctiva, cornea, iris, and natural crystalline lens. Record all preoperative baseline clinical observations and the clinical significance of each observation. Give consideration to Inclusion/Exclusion criteria (refer to *Section 10: Subject Population*).

*NOTE:* Certain pathologies may become apparent after cataract extraction and IOL implantation. In these instances, the preoperative pathology status should be updated.

## 12.1.1.12 Crystalline Lens Assessment

Assess cataract grade using LOCS II classifications (Chylack 1989). Refer to MOP (*LOCS II Instructions for Grading*) for detailed grading instructions.

## 12.1.1.13 Inflammatory Signs

Grade inflammatory signs including cells and flares, and corneal edema. Refer to MOP (*Inflammatory Signs Grading*) for details including grading scale.

**Document:** TDOC-0050176 **Version:** 2.0; Effective; CURRENT

Status: Effective Page 39 of 75

#### 12.1.1.14 Dilated Fundus Examination

Perform a dilated fundus examination (indirect and direct ophthalmoscopy). Record diameter of dilated pupil. Record all preoperative baseline clinical observations with consideration given to the inclusion and exclusion criteria (Refer to *Section 10. Subject Population*) and note clinical significance.

**NOTE:** Certain pathologies may become apparent after cataract extraction and IOL implantation. In these instances, the preoperative pathology status should be updated.

#### 12.1.1.15 Randomization

Randomization should be undertaken within 2 business days of the operative visit. Ensure that all inclusion/exclusion criteria have been met and that all preoperative (Visit 0) assessments have been performed. Utilize the IRT system to randomize subject's study eye to the test or to the control group.

#### **12.1.1.16 Adverse Events**

Record AEs as described in Section 13: Device Deficiencies and Adverse Events.

#### 12.1.2 Operative Visit (Visit 00 – Day 0, Unilateral)

## **12.1.2.1 Medical History**

Update subject's ocular and non-ocular medical history.

#### 12.1.2.2 Ocular and Non-ocular Concomitant Medication

Record changes in ocular and non-ocular concomitant medications.

**NOTE:** Routine preoperative and intra-operative medications do not require capture.

#### 12.1.2.3 Inclusion/Exclusion Criteria

Refer to the list of Inclusion/Exclusion criteria in *Section 10: Subject Population*. Ensure the subject still meets all requirements for participation and eligibility.

## **12.1.2.4** Surgery

**NOTE:** Prior to performing study surgeries, surgeons should have a minimum experience of 100 cases with the Infiniti® Vision System and 100 cases with the Centurion® Vision System.

Document: TDOC-0050176 Version: 2.0; Effective; CURRENT

Status: Effective Page 40 of 75

Confirm subject meets all inclusion/exclusion criteria (refer to *Section 10: Subject Population*), and has been randomized (refer to *Section 12.1.1.17. Randomization*) prior to proceeding with surgery.

Care should be taken to protect endothelium with the Ophthalmic Viscosurgical Device, VisCoat®. As the nuclear disassembly is performed, reapplication of the VisCoat® should be done throughout the procedure in order to protect the endothelium. The surgeon should create a working space each time before re-engaging the ultrasound.

**NOTE:** Prepare subject for surgery per site specific standard operating procedures. Manually create a 5.0 to 5.5 mm capsulorhexis and proceed with phacoemulsification as specified by randomization.

Femtosecond laser use at any point in the surgery (eg, incision, capsulotomy, lens fragmentation, etc) is prohibited. Additionally pre-chop nucleofracture technique is prohibited. The IOL implantation needs to be managed either with Alcon Monarch® IOL injector (or the INTREPID® AutoSert® IOL injector) and the same cartridge D (2.2-2.4 mm).

## 12.1.2.4.1 Problems During Surgery

Indicate what problems, if any, occurred during surgery.

## 12.1.2.4.2 Other Procedures at Surgery

Indicate other procedures, if any that occurred at the time of surgery. Other procedures include those performed outside of routine cataract surgery.

*NOTE:* Other planned procedures at the time of surgery are exclusionary (Refer to *Section 10: Subject Population*).

#### 12.1.2.4.3 Lens Information

Document details of the IOL implanted including IOL model and brand in the medical notes.

## 12.1.2.4.4 Successful Placement of IOL in Capsular Bag

Indicate in the medical notes if IOL placement in the capsular bag was successful.

**Document:** TDOC-0050176 Version: 2.0; Effective; CURRENT

Status: Effective Page 41 of 75

## 12.1.2.5 Programmable Phacoemulsification Settings

Document whether preferred pre-programmed phacoemulsification machine settings were altered prior to or during the surgical procedure. If settings were altered, indicate the setting(s) modified.

#### 12.1.2.6 Phacoemulsification Metrics

## 12.1.2.6.1 Cumulative Dissipated Energy (CDE)

At the conclusion of the surgery, record CDE as reported on the Vision System interface.

#### **12.1.2.6.2 BSS Fluid Use**

Weigh the empty drain bag in preparation for the total BSS consumption calculation. Refer to the MOP for calculation details.

*NOTE:* It is preferable to use the same BSS Bags (BSS or BSS Plus) for all the case.

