### 7 INTRODUCTION

# 7.1 Background

Cataract surgery is a commonly performed procedure with over 5.0 million cases performed annually worldwide. Modern cataract surgery utilizes small incision and phacoemulsification surgical techniques to emulsify and aspirate the cataractous lens for implantation of a foldable intraocular lens (IOL).

The Centurion® Vision System [510(k) Number: CVS K121555, US-FDA approved in December 2012] is a new phaco-emulsifier aspirator manufactured by Alcon. The system incorporates Active Fluidics™ control system that maintains a stable surgical IOP despite variations in aspiration flow rate. A more stable surgical IOP allows the surgeon to experience less movement of ocular structures, as well as the option to lower the IOP setting. This coupled with the higher resistive aspiration tubing coupled with lower compliant aspiration tubing and Active Fluidics™ minimize occlusion break surge. The system is capable of creating significantly higher vacuum levels which creates higher tip holding forces. Previous studies have indicated that higher vacuum correlates to a lower Cumulative Dissipative Energy (CDE), which is a measure of the amount of energy dissipated at the incision. The metric also correlates to how much energy is required to perform the surgery. This study will be assessing the CDE as well as measuring the total BBS fluid used during the surgical procedure.

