# 8.4 Study Endpoints

# 8.4.1 Effectiveness Endpoints

Cumulative Dissipated Energy (CDE) - CDE is a metric displayed on the system user interface of both the Centurion® and Infiniti® systems. CDE represents the energy dissipated of the u/s tip and infusion sleeve at the 'incision point' defined as 5.6mm behind the cutting edge. It reflects the total of CDE (ie, CDE longitudinal + CDE torsional).

**Document:** TDOC-0050176 **Version:** 2.0; Effective; CURRENT

Status: Effective Page 25 of 75

 $CDE = CDE_{long} + CDE_{Tor} = (Longitudinal Time x Average Longitudinal Power) + (Torsional Time x 0.4 x Average Torsional Amplitude)$ 

CDE will be used as both a *primary or secondary endpoint*, depending on the objective.

**BSS Fluid Used** - BSS Fluid will be measured by weighing the BSS bag after priming. The BSS bag will then be re-inserted and the system will then require a re-prime. A clamp will be temporarily used on the administration tubing to prevent fluid from being pulled from the bag. The BSS bag will be weighed after the case.

BSS fluid used corresponds to the total fluid through the anterior chamber.

DSS fluid used corresponds to the total fluid unrough the affection chamber.
is a function of Aspiration Flow Rate, and Pump modulation. The Pump modulation varies as tissue is occluded and unclouded against the tip.
Incision Leakage is a function of surgical IOP, incision size, incision construction, and how the phaco hand-piece and 2 nd instrument is used.
A reduction in BSS Fluid Used implies less induced trauma to tissues. BSS Fluid Used will be used as a secondary endpoint.

Alcon - Business Use Only Protocol - Clinical

Document: TDOC-0050176 Version: 2.0; Effective; CURRENT

Status: Effective Page 26 of 75

Effective Date: 18-Jul-2016

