7	C. Ensure correct Doctor and Procedure setting are selected. Press Prime FMS on the Setup screen to initiate priming/test sequence.  After successful completion of the priming/test sequence, the prime status indicator will change from NOT PRIMED (red) to PRIMED (Green). If the priming/test sequence fails, an advisory message will be displayed. When prime is complete, Setup will automatically switch to Fill step but will not activate until the Fill button is pressed.	Circulator or Scrub Nurse

Document: TDOC-0050176 Version: 2.0; Effective; CURRENT

Status: Effective Page 71 of 75

Effective Date: 18-Jul-2016

Ultrasound Handpiece Setup	
8. Thread U/S Tip onto U/S handpiece. Tighten firmly, using the Tip Holder/Wrench. Remove Tip Holder/Wrench and retain for future tip removal. Match the proper color coding for the Ultrasonic Tip and the corresponding Infusion Sleeve per section D in PRECAUTIONS AND WARNINGS.	Scrub Nurse
9. Thread Infusion Sleeve onto the handpiece, over the U/S Tip. Sleeve end should clear bevel on U/S Tip by 1-2 mm. Avoid twisting of the Sleeve. NOTE: Infusion Sleeves fit over both U/S and I/A tips. Orient port holes as shown:  ASSEMBLY TO U/S HANDPIECE  Nose Cone Recess  U/S Tip  Infusion Sleeve  Infusion Sleeve  Flared Kelman® Straight  Kelman® Straight	Scrub Nurse
10. Connect male irrigation line luer fitting (Gray) and female aspiration line luer fitting (Blue) to U/S handpiece. For U/S handpieces equipped with a locking irrigation port, turn the white luer lock clockwise to tighten and lock fitting to handpiece.	Scrub Nurse
11. Prepare handpiece for tuning and flow check. To allow irrigation fluid to flow from U/S tip, press Fill button on front panel or use the remote control to scroll to Fill and press Enter. Fill Test Chamber. Observe the stream of irrigating fluid from the irrigation and aspiration ports when the Fill button is depressed.  If the stream of fluid is weak or absent, good fluidics response will be jeopardized. Good clinical practice dictates the testing for adequate irrigation and aspiration flow prior to entering the eye.	Scrub Nurse or Surgeon
12. Slide Test Chamber over Infusion Sleeve making sure that no air bubbles are present. Place handpiece vertically in the pouch created by the Tray Support Cover with Test Chamber pointing upwards.  Place handpiece vertically in pouch over handpiece tip  Slide test chamber over handpiece tip	Scrub Nurse

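### Does weighing the empty drain bag mean that BSS fluid used is measured in two conflicting ways?

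*Protocol*

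**What the plan says.** Protocol 8.4.1 defines the endpoint on the supply side: "BSS Fluid will be measured by weighing the BSS bag after priming". The bag then goes back into the console, the system is primed again, and the bag is weighed a second time once the case is over. For the re-prime, "A clamp will be temporarily used on the administration tubing to prevent fluid from being pulled from the bag".

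Protocol 12.1.2.6.2, the visible surgery-day instruction, reads "Weigh the empty drain bag in preparation for the total BSS consumption calculation". Its next sentence sends the reader to the Manual of Procedures (MOP) for the calculation, and Protocol 12.1 says more generally that the MOP holds the full description of assessments.

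SAP 4.1 splits BSS used into incision leakage plus aspirated fluid, with a large redaction directly below. The replacement wording in SAP 8.2 gives one formula per console. For Centurion it is the bag's post-prime weight minus its post-surgery weight, less 0.5 ml. For Infiniti it is the same difference for a bottle, with no deduction. SAP 8.2 also says that Version 3.0 corrected the calculation of estimated incision leakage; text on either side of the two formulas is redacted.

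**The concern.** Read alone, 12.1.2.6.2 assigns total BSS consumption to a container that 8.4.1 and the SAP never use for it. The two are not interchangeable. If the drain bag receives only aspirated fluid, its weight leaves out whatever escaped through the wound. Protocol 8.4.1 says "Incision Leakage is a function of surgical IOP, incision size, incision construction", and Protocol 7.1 describes Centurion as giving the surgeon a more stable surgical IOP "as well as the option to lower the IOP setting". Omitted leakage could therefore differ by console, which is the contrast tested in hypotheses 2 and 3.

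Three smaller points seem to loosen the definition further:

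- 8.4.1 speaks only of a bag, but the SAP formula for Infiniti uses a bottle.
- The post-prime time point looks open. The attached Centurion pack directions have a separate step after priming: "When prime is complete, Setup will automatically switch to Fill step but will not activate until the Fill button is pressed", and later "To allow irrigation fluid to flow from U/S tip, press Fill button on front panel".
- The 0.5 ml deduction applies to Centurion only, and no reason for it is visible.

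Both hypotheses are tested confirmatorily at one-sided 0.05. The weights are taken once, on the day of surgery, and missing values are not imputed, so a weight not taken would be lost.

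**Working it through.** **1. The plan's own figure.** Protocol 15.10 and SAP 6 size the trial on CDE: difference 7.4, SD 15.2, one-sided 0.05, 80% power.

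n per group = 2 × (1.645 + 0.842)² × (15.2 / 7.4)² = 2 × 6.183 × 4.219 = 52.2, rounded up to 53. Exact t power at 53 is 80.1%. Then 53 / 0.90 = 58.9, rounded up to 59, and 3 × 59 = 177.

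The figures reproduce. They concern CDE, which is read from the console display (Protocol 12.1.2.6.1) and does not depend on any weighing. No power or SD is stated for BSS.

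**2. The texts side by side.**

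| Place | Container | Weights named | Used for |
|---|---|---|---|
| Protocol 8.4.1 | Supply bag | After prime and after case | BSS used |
| SAP 8.2, Centurion | Supply bag | After prime and after surgery, less 0.5 ml | BSS used |
| SAP 8.2, Infiniti | Supply bottle | After prime and after surgery | BSS used |
| Protocol 12.1.2.6.2 | Drain bag | Empty only | Preparation; calculation in the MOP |

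A volume from the drain bag would need its full weight minus its empty weight. Only the empty weight appears. The three rows that define BSS used agree with one another and contain no drain-bag term. To obtain the endpoint from the drain bag, a site would have to add a weighing that no visible text requests and set aside the definition in 8.4.1.

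**3. What the tare is probably for.** By the SAP 4.1 identity, leakage = BSS used − aspirated fluid. If the drain bag holds the aspirated fluid, its tare is needed to estimate leakage, which SAP 8.2 names as a calculated quantity. That fits the redactions around those formulas, but it is an inference.

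**4. Size if the endpoint did come from the drain bag.** Let δ be an *assumed* arm difference in omitted leakage, in SDs of BSS used. With 53 per arm, √(53/2) = 5.148, and the error rate is Φ(±5.148 δ − 1.645).

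| δ (assumed) | Centurion leaks more | Infiniti leaks more |
|---|---|---|
| 0.05 | 0.08 | 0.03 |
| 0.10 | 0.13 | 0.02 |
| 0.20 | 0.27 | below 0.01 |

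A true effect with 80% power (0.49 SD) would have about 91% or 63% power at δ = 0.10, in the same order. These are properties of any two-group test with a bias of that size. Nothing in the documents fixes δ or its sign.

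**5. The smaller points.**

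- *Fill step.* Only a Centurion pack leaflet is attached; the Infiniti leaflet covers handpiece care. No arm difference in fill volume can be shown. Weighing after fill and test would also clash with 8.4.1, where re-inserting the weighed bag forces a re-prime, and with the SAP's post-prime baseline.
- *0.5 ml.* Adding it back to every Centurion value raises the Centurion minus Infiniti difference by exactly 0.5 ml and leaves its standard error unchanged. A reader can undo it by hand.
- *Bottle.* The SAP names it, and the Infiniti formula has the same form as the bag formula.

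**The case for a change.** The best argument for a change is that surgical staff are likely to follow the visit-by-visit section, and the visible text there names only the drain bag and ties it to *total* consumption. The MOP is not available, so it cannot be shown to correct the impression. The two SAP formulas are visible only as replacement wording in the revision history, because the body text that would hold them is redacted. A supply weight missed on the day cannot be recovered, and tidying the text would cost a few lines.

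Much of this is true as description. The wording of 12.1.2.6.2 is loose, and a cross-reference to 8.4.1 would read better. The argument does not show that following the plan gives a wrong endpoint. Protocol 8.4.1 is current text and by itself requires both supply weights. A section that prepares one container and passes the calculation to a manual does not replace that definition. That 12.1.2.6.2 is the only surgery-day instruction can be said only of the visible text, since the phacoemulsification metrics row in the SAP appendix schedule has a redacted entry beside BSS fluid use.

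**Conclusion.** No change is needed. The endpoint of hypotheses 2 and 3 is defined consistently from supply-container weights in Protocol 8.4.1 and in the visible SAP formulas. The drain-bag sentence in 12.1.2.6.2 is loosely worded detail that sites resolve through the MOP; it is not a rival definition. The error rates from below 0.01 to 0.27 depend on a drain-bag endpoint that the plan does not describe and on leakage differences in SD units that the documents do not supply, so they do not measure a defect. CDE, the 53 per group and the primary test are unaffected.

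This rests on two assumptions that the documents cannot confirm: that the MOP follows 8.4.1, and that the drain-bag tare serves aspirated volume or estimated leakage. If the MOP did compute BSS used from the drain bag, the conclusion would have to be revisited. A note on the purpose of that weight, or on the basis of the 0.5 ml, would be an editorial courtesy that alters no result.
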